4.2.3.2.5. Global evaluation of therapy tolerability by the patient and the physician

Global evaluation of study drug tolerability should be made by the patient and Investigator according to the following scale:

Scores	Evaluation
0	Poor
1	Satisfactory
2	Good
3	Excellent

Evaluation of the study drug tolerability by the patient and the physician (points/scores) should be specified in the eCRF at Visits 2 or 3 (where applicable).

4.2.4 Trial stages

4.2.4.1 Screening/randomization/therapy initiation (Visit 1)

Visit 1 is scheduled for Day 1. At this visit, the doctor evaluates the patient's eligibility for the trial. If no non-inclusion criteria are met, the patient undergoes randomization with further training on the drug use and handling precautions, is given the study drug/comparator drug and a patient's diary, and is instructed on the patient's diary completion requirements.

Screening visit procedures:

- Signing of the Informed Consent Form;
- Demographic data (date of birth, sex, age);
- Measurement of weight and height;
- Anamnesis gathering;
- Records on the concomitant therapy;
- Evaluation of inclusion/non-inclusion criteria;
- Evaluation of the throat pain intensity according to VAS;
- Fill-in of TSS questionnaire by the Investigator;
- Physical examination (including oropharynx);
- Measurement of the main vital signs;
- Hematology;
- Biochemistry;
- Urine pregnancy test;
- 12-lead ECG;
- Evaluation of inclusion/non-inclusion criteria;
- Randomization;
- Training for administration and handling of the study drugs;
- Dispensing of the study drugs;
- Provision with the patient's diaries and training on the fill-in rules;
- Initiation of therapy with the study drugs;
- Evaluation of adverse events (including based on results of the throat and pharynx examination).

Taking into account a dosage form of the study drugs (topical spray), the patients will be instructed on the use and handling the sprinkler, as well as the oral spraying technique. The first dose of the drug will be taken at the trial site under the Investigator's supervision. The patients will be told to turn the tube perpendicularly to the bottle (vial) before the first use. The patient should open his/her mouth wide, direct sprayer towards the pharynx, and press

the sprinkler nozzle. The patient should hold their breath during spraying. After each use, the tube should be turned back down to block the spraying nozzle.

The patients will be also instructed on the sprinkler handling and care rules. In the event that Angal S/ANTI-ANGIN® FORMULA spray will not be used for some time, it is recommended to clean the spray nozzle after the last use according to the following procedure:

- 1. The spray should be turned upside down, and the actuator button should be pressed until the solution remaining in the spraying adapter is removed (solution does not spray out anymore).
- 2. The tube should be removed from the spraying nozzle bottle and put in the container filled with warm water for a few minutes.
- 3. The tube should be taken out of water and allowed to dry.
- 4. To block the spray nozzle, the dried tube should be put on the spraying nozzle so that it faces downwards.

In case of the actuator (sprinkler) failure, the patient should contact the Investigator.

4.2.4.2 Efficacy evaluation visit (Visit 2, Day 4)

Visit 2 is conducted on Day 4; the patient must visit the trial site in the fasted state and bring the filled-in diary and unused drug.

If Group B patients (ANTI-ANGIN® FORMULA) did not meet recovery criteria (total $TSS \le 2$) at Visit 2 (Day 4), they will require continuation of the therapy, and some procedures for those patients will be transferred for the next day (Visit 3, Day 5), see below. The patients will keep their diaries and the unused drugs.

Visit 2 procedures for both groups:

- Collection of complaints, actualization of anamnesis;
- Records on the concomitant therapy;
- Physical examination (including oropharynx);
- Measurement of the main vital signs;
- Evaluation of adverse events (including based on results of the throat and pharynx examination);
- Evaluation of exclusion criteria;
- Compliance evaluation (diary completion, administration of the study drugs);

Visit 2 procedures for patients from Group A (Angal S) and Group B (ANTI-ANGIN® FORMULA) who achieved recovery criteria (total TSS \leq 2):

- Hematology;
- Biochemistry;
- 12-lead ECG;

- Global evaluation of treatment tolerability during the trial by the physician and the patient;
- Return of the unused study drug;
- Return of the patient's diary;

4.2.4.3 Trial completion visit for Group B patients (Visit 3, Day 5)

This visit is for Group B patients only (ANTI-ANGIN® FORMULA) who did not achieve the recovery criteria (total TSS score ≤ 2) at Visit 2 (Day 4).

Visit 3 is conducted on Day 5; the patient must visit the trial site in the fasted state and bring the filled-in diary and unused drug.

Visit 3 procedures:

- Collection of complaints, actualization of anamnesis;
- Records on the concomitant therapy;
- Physical examination (including oropharynx);
- Measurement of the main vital signs;
- Evaluation of adverse events (including based on results of the throat and pharynx examination);
- Evaluation of exclusion criteria;
- Return of the unused study drug;
- Return of the patient's diary;
- Compliance evaluation (diary completion, administration of the study drugs);
- Hematology:
- Biochemistry;
- 12-lead ECG;
- Global evaluation of treatment tolerability during the trial by the physician and the patient.

4.2.4.4 A follow-up visit (Visit 4)

A follow-up visit shall be conducted by phone to find out about the patient's state and any AEs. A visit 2 days after the therapy completion visit (e.g., on Day 6 or 7, depending on the arm and therapy duration).

Follow-up visit procedures (by phone):

• Evaluation of adverse events (without the throat and pharynx examination).

In case of adverse events, the patient might be invited to visit the trial site.

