3.2 Trial goals

Primary goal:

• Evaluation of non-inferiority of the therapeutic efficacy of Angal S, topical spray [menthol], containing 0.5 mg of lidocaine hydrochloride and 2 mg of chlorhexidine digluconate per 1 ml (Sandoz d.d., Slovenia); one dose includes 3 to 5 consecutive presses on the actuator button, six to ten times per day, for 4 days or until full recovery (whichever occurs first during 4 days of therapy), compared to ANTI-ANGIN® FORMULA, topical metered spray, containing 0.12 mg of tetracaine hydrochloride and 0.24 mg of chlorhexidine bigluconate per dose (OOO Valeant, Russia); one dose includes 1 to 2 consecutive presses on the actuator button, up to 6 times per day, for 5 days or until full recovery (whichever occurs first during 5 days of therapy), in patients with uncomplicated, acute, infectious and inflammatory diseases of the pharynx accompanied by a sore throat.

Secondary goals:

• Evaluation of safety of Angal S, topical spray [menthol], containing 0.5 mg of lidocaine hydrochloride and 2 mg of chlorhexidine digluconate per 1 ml (Sandoz d.d., Slovenia); one dose includes 3 to 5 consecutive presses on the actuator button, six to ten times per day, for 4 days or until full recovery (whichever occurs first during 4 days of therapy), compared to ANTI-ANGIN® FORMULA, topical metered spray, containing 0.12 mg of tetracaine hydrochloride and 0.24 mg of chlorhexidine bigluconate per dose (OOO Valeant, Russia); one dose includes 1 to 2 consecutive presses on the actuator button, up to 6 times per day, for 5 days or until full recovery (whichever occurs

first during 5 days of therapy), in patients with uncomplicated, acute, infectious and inflammatory diseases of the pharynx accompanied by a sore throat.

- Evaluation of adverse events (AEs) in the trial arms.
- The AEs rate comparison between the trial arms.

Protocol No. TE 003 ANG LSP

4 Trial design

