4.5 Expected duration of the subjects' participation in the trial

Screening period: 1 day.

Treatment period: up to 5 days (including the screening/randomization day).

Follow-up period: up to 2 days.

A maximum duration of each subject's participation: 7 days.

A minimum duration of each subject's participation: 6 days (depending on the arm).

4.6 Description of rules for termination of the trial parts or the trial as a whole

The trial may be terminated on the following grounds:

- 1. Upon the Sponsor's initiative: availability of new toxicological or pharmacological data, or data on SAE which require re-consideration of the previous evaluation of the benefit/risk ratio.
- 2. Upon the Sponsor's initiative: AEs incidence or severity require the trial termination;
- 3. Upon the Sponsor's initiative: other reasons including administrative ones.
- 4. Upon the decision of the regulatory authorities.

The trial may be terminated at a specific trial site in case the patients enrollment or data quality are unsatisfactory, or it is reasonable to assume a breach of GCP and/or Declaration of Helsinki, or other serious protocol deviations.

In case of early termination of the trial, the Sponsor must inform the trial site personnel as well as regulatory authorities with indication of the reason thereof.

The rules for trial termination for every participant are described in Section 5.3.

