9.1.4 Safety parameters analysis

A descriptive part of the safety analysis will include an evaluation of incidences and two-sided CI 95% for the following parameters in every trial group:

- AEs: the incidence in total and for separate categories (according to MedDRA), for the trial and by groups;
- SAEs: the incidence in total and for separate categories (according to MedDRA), for the trial and by groups;
- Incidence of clinically significant changes of the physical examination results by visits and groups;
- Incidence of clinically significant changes of the laboratory results by visits and groups;
- Incidence of clinically significant changes of the vital signs (body temperature, BP, pulse rate, HR) by visits and groups;
- Incidence of clinically significant changes of the ECG parameters by visits and groups;
- Global tolerance evaluation during the trial by the Investigator and patient.

The Fisher's exact test will be used to compare incidences between the groups, and chi-square will be used to compare the global therapy tolerability by the Investigator and patient. The McNemar's test will be used to evaluate for the dynamic changes during the trial (before—after) for all the repeatedly evaluated incidences in every group.

In addition to the incidence, all the quantitative safety parameters will be presented in a table form (laboratory results, vital signs, ECG) by visits and groups. The difference will be evaluated using 2-way-ANOVA (group and visit numbers will serve as the relevant factors). The post-hoc criteria will be used in case of significant difference.

Safety analysis will be performed on the safety population.

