4.1.4 Safety and tolerability analysis

AEs incidence will be compared between the trial arms using Pearson's chi-squared test. In case of significant changes, a relative risk will be calculated (with 95% CI).

A tolerability level for every group will be calculated based on the AEs incidence and nature (in accordance with Section 2.3 of this Plan).

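### Adverse event incidence is compared between arms without a common window, although unrecovered Group B patients have one more examination and one more day of follow-up; the tilt towards Angal S is small

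*Protocol*

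**What the plan says.** - **Goal.** Protocol section 3.2 lists among the secondary goals: "The AEs rate comparison between the trial arms".
- **Extra visit.** Section 4.2.4.3 restricts Visit 3 (Day 5) to one part of one arm: "This visit is for Group B patients only (ANTI-ANGIN® FORMULA) who did not achieve the recovery criteria" at Visit 2. Its procedures include "Evaluation of adverse events (including based on results of the throat and pharynx examination").
- **Last contact.** Section 4.2.4.4 sets the timing of the phone call: "A visit 2 days after the therapy completion visit (e.g., on Day 6 or 7, depending on the arm and therapy duration"). At the call there is "Evaluation of adverse events (without the throat and pharynx examination").
- **Participation.** Section 4.5 gives a minimum of 6 days, depending on the arm, and states: "A maximum duration of each subject's participation: 7 days".
- **AE collection.** Section 8.3.4 runs AE recording from consent to each subject's own completion of the trial. It names no day common to both arms. SAP section 3.8 fixes only the baseline visit.
- **Tests.** Protocol section 9.1.4: "The Fisher's exact test will be used to compare incidences between the groups". SAP section 4.1.4: "AEs incidence will be compared between the trial arms using Pearson's chi-squared test". Neither provides for time observed, a common cut-off or a sensitivity analysis on follow-up.

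**The concern.** A crude incidence counts patients with at least one event, so it rises with the length of observation and with the number of times a patient is examined. Here both are greater in one arm only, and within that arm for the patients still ill on Day 4. An unrecovered Group A patient gets neither the extra examination nor the extra day. Background events and minor local findings can therefore only be added to the comparator's count. At stake is the fairness of a comparison that the protocol names as a goal, in an open-label trial where the tilt favours the sponsor's product.

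**Working it through.** **Inputs from the documents.** Last site visit: Day 4 (Group A and recovered Group B) or Day 5 (unrecovered Group B). The phone call follows two days later. There are 140 patients per arm.

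**Inputs that are assumptions.** The share *u* of Group B with TSS above 2 on Day 4, the AE incidence in Group A, and a constant daily AE hazard that is equal in both arms. The documents give none of these.

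**1. The plan's own figures.** Day 4 + 2 = Day 6 and Day 5 + 2 = Day 7, which agrees with the 6 and 7 days in section 4.5. An unrecovered Group B patient has 7 calendar days against 6 (7/6 = 1.17), or 6 elapsed days against 5 (6/5 = 1.20). Such a patient has three site examinations (Visits 1, 2 and 3) instead of two.

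**2. Mean observation in Group B.** This is 6 + *u* days, against 6 in Group A. For *u* = 0.3 to 0.5 it is 6.3 to 6.5 days, a ratio of 1.05 to 1.083.

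**3. Expected incidence with no true difference.** Let Group A show 10% by Day 6.
- An unrecovered Group B patient, seen to Day 7: 1 − 0.9^(7/6) = 11.57%.
- Group B overall: (1 − *u*) × 10% + *u* × 11.57%.

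| *u* | Group B incidence | Excess (points) | Extra patients in 140 |
|---|---|---|---|
| 0.12 | 10.19% | 0.19 | 0.26 |
| 0.30 | 10.47% | 0.47 | 0.66 |
| 0.50 | 10.78% | 0.78 | 1.10 |

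On elapsed days, 1 − 0.9^(6/5) = 11.88%, and the excess at *u* = 0.3 and 0.5 becomes 0.56 and 0.94 points.

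**4. Wider range.** With Group A incidence of 5% to 20% and *u* from 0.10 to 0.60, the excess from time alone is 0.1 to 2.1 points.

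**5. Effect on the test.** Take 10% incidence, elapsed days and *u* = 0.37. The last value is 1 − 0.63, from the planned sore-throat-free rate, which is a different criterion from TSS of 2 or less. For the two-sided 5% chi-squared test with 140 per arm, exact enumeration gives:
- chance of a false finding of more AEs in Group B: from 2.4% to 3.7%;
- chance of a false finding of more AEs in Group A: from 2.4% to 1.5%.

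**6. Detection.** The documents give no basis for a figure. As an illustration only, if the extra visit raised detection in unrecovered patients by 25%, Group B would show 11.8% and the first error rate would be 6.8%.

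**7. After the change.** When events are counted to the same day in every patient, the time-related ratio returns to 1.00. The extra Day 5 examination is not removed by any cut-off that includes Day 5.

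**The case against.** The strongest reply is that one follow-up rule applies to everybody: two days after the last scheduled site visit. The windows differ because the regimens differ, and section 3.2 compares those regimens with their durations named. **This stands in part.** A reader might infer that the whole excess in Group B would be artefact. The documents do not support that, because an AE caused by the comparator's additional treatment day belongs to the comparison that was planned. Only background events on the extra day and additional detection are bias.

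Other points also stand:
- **Less is added than the schedule suggests.** Under section 4.2.4.2, hematology, biochemistry, ECG and the tolerability rating move from Day 4 to Day 5 for these patients. What is added is the complaints, the physical and throat examination, vital signs and AE questioning. Unscheduled visits are open to both arms.
- **The unrecovered share may be low.** In the lozenge trial cited in section 9.2, (11 + 1)/104 = 11.5% had moderate or severe sore throat on Day 4, and a mild residual sore throat alone is compatible with recovery. Other TSS items could raise the share, so it is unknown. The 0.12 row above shows the effect near that value.
- **Little depends on the test.** SAP section 4 bases the non-inferiority conclusion on the primary parameter alone and gives the safety variables an exploratory role.

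What the reply does not remove is that background events and extra findings are counted more fully in one arm, and that neither document acknowledges this in the analysis.

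**Conclusion.** The asymmetry is explicit in the schedule and its direction is known: it slightly favours Angal S. From time alone it is about 0.5 to 0.8 points at an assumed 10% incidence and an assumed 30% to 50% unrecovered, or roughly one patient in 140. It is smaller if fewer are unrecovered. The detection effect of the extra examination comes on top and cannot be quantified from the documents.

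A reader might go further and infer that the safety comparison is invalid or that the non-inferiority result is compromised. Neither follows. The time effect is small, part of any excess would be a true regimen effect, and the primary endpoint is assessed on Day 4 in both arms. Severity is minor. The case for a change is that it is cheap and removes an avoidable question.

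**What to change.** In Protocol section 9.1.4 and SAP section 4.1.4:

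1. Keep the full-period AE comparison and label it as the comparison of the two regimens.
2. Add a between-arm comparison of AEs with onset from first dose to the end of Day 5, and list later events by arm. The end of Day 5 precedes every patient's last phone contact, so the window is ascertained in all. The end of Day 6 would not do: Group A is phoned during that day, while unrecovered Group B patients are asked about all of it on Day 7.
3. Add a sensitivity analysis that flags or excludes AEs first found at the Visit 3 examination. Some of these would have been reported by phone anyway, so exclusion errs in the other direction.
4. State the unequal follow-up wherever AE incidences are reported.
5. Confirm that the eCRF captures AE onset date. It is implied by AE duration (Protocol section 4.1.2) and by the separation of events before and after first dose (section 8.3.4), but it is not stated.

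The two documents should also name the same test, since one has Fisher's exact test and the other Pearson's chi-squared.

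**Cost.** A few SAP sentences, one filter on onset date and a little more analysis. Late events do not count in the common-window comparison, which is why the full-period tables and the listing stay. No visit, procedure or sample size changes.

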4.2.4.5 Unscheduled visits

The unscheduled visits will be conducted when necessary, e.g., in case of the index disease deterioration, AEs, or the study drug (Angal S or ANTI-ANGIN® FORMULA) intolerability.

Every unscheduled visit, irrespective of its cause, must include the procedures listed below with completion of the relevant eCRF pages (Unscheduled Visit):

- Physical examination (including topical examination);
- TSS evaluation;
- Measurement of the main vital signs (blood pressure, heart rate, breathing rate, body temperature);
- 12-lead ECG (if it has not been done for the last 12 hours);
- Evaluation of adverse events;
- Evaluation of the concomitant therapy.

Other diagnostic and treatment procedures may be conducted depending on clinical situation and upon the Investigator's decision.

Taking into account frequency of visits, unscheduled visits may be conducted on the same days as scheduled ones but in a different time (e.g., in case of worsening the patient may visit the center in afternoon). All procedures for the scheduled visits are identical for both arms at every trial stage, except for the Group B patients who, if the recovery criteria (total $TSS \le 2$) are not met at Visit 2 (Day 4), should continue the trial therapy and visit the trial site for scheduled Visit 3 (Day 5).

4.2.4.6 Visit of premature discontinuation of the trial

Visit 2 procedures will be applied for the visit of premature discontinuation.

4.3 Subjectivity minimization/elimination measures

4.3.1 Randomization

This will be an open, randomized trial. Every screened patient will be assigned with an individual registration number containing the initials (name, patronymic, surname) and a participant's number assigned to every new screened patient in a three-digit format (001, 002, etc.). The patients who meet the inclusion criteria at the screening visit will be randomized to a study drug group or a comparator drug group using the envelope method. For the purposes of randomization, a list of randomization numbers for the envelops will be generated,

every number will correspond to a study drug group or a comparator drug group.

4.3.2 Blinding methods

This trial will be conducted without blinding (an open trial).

4.4 Description of the drugs used in the trial

4.4.1 Dosage form

Study drug: Angal S, topical spray [menthol], containing 0.5 mg of lidocaine hydrochloride and 2 mg of chlorhexidine gluconate in 1 ml. Clear, colorless solution with an odor of peppermint and ethanol, and taste of menthol.

Reference (comparator) product: ANTI-ANGIN® FORMULA, metered topical spray, containing 0.12 mg of tetracaine hydrochloride and 0.24 mg of chlorhexidine gluconate in 1 dose. Colorless, mint-flavored liquid.

4.4.2 Packaging

Study drug: A bottle (vial) made of amber glass, hydrolytic resistance of the inner glass surface Class III, containing 30 ml of solution. A screw cap with mechanical sprayer and spraying adapter with parts made of PPL, PE, stainless steel, and acetal resin.

Reference (comparator) product: 25 ml of the drug (spray) are placed in a plastic bottle with a dosing valve in a carton pack with Prescribing Information.

4.4.3 Labeling of the study drugs

As this is an open trial, the trial site will be provided with the packed products from the series commercially available in the EU (study drug) and Russia (comparator drug). Every carton box with the drugs will contain a self-adhesive label with the data listed below:

- "For clinical trials only";
- A protocol number;
- Title, address, and phone number of the trial site;
- Title, address, and phone number of the trial Sponsor;
- A field for a patient's randomization number.

The label should not overlap the drug name, active substances, and their strength, shelf life, manufacturer's name.

At the screening visit, every patient in the study drug group will be given 1 bottle (vial) of Angal S (150 doses), and every patient in the comparator drug group will be given 1 bottle (vial) of ANTI-ANGIN® FORMULA (100 doses). The dispensed

amounts are sufficient for the trial completion according to the protocol.

